	antifibrotic treatment between October 1, 2014 and April 30, 2018. Patients will be divided into three mutually exclusive cohorts: (1) nintedanib initiators; (2) pirfenidone initiators; and (3) control cohort who received no prescription antifibrotic treatment during selection window.										
Variables:	The following demographic and clinical characteristics as well as medical interventions for IPF during the 12-month baseline period (pre-treatment) will be evaluated and compared between cohorts 
 Demographic characteristics (e.g., age, gender, race/ethnicity, geographic region, insurance type) Clinical characteristics (e.g., selected comorbidities, baseline weight and body mass index [BMI], blood pressure, smoking status, laboratory measures, pulmonary function tests) Pharmacological interventions (e.g., index medication dose, time from the earliest diagnosis of IPF to index medication, other IPF treatments, bronchodilators, corticosteroids) Non-pharmacological interventions (e.g., surgical procedures, supportive therapies, diagnostic procedures) 										
Data sources:	GE Centricity EMR database from October 2013 to April 2018										
Study size:	A preliminary analysis identified 868 IPF patients with pirfenidone, 615 patients with nintedanib, and about 10,000 untreated patients.										
Data analysis:	Patient demographic and clinical characteristics will be described using descriptive analyses. Counts and percentages for categorical variables and measures of central tendency (mean, median, standard deviation [SD], and min/max) for continuous variables will be reported. Differences between the treatment cohorts (compared to each other and to untreated patients) will be assessed using absolute standardized differences and p-values. The probabilities of receiving one treatment over another will be tested by propensity scores and using multivariable logistic regression adjusted for key baseline characteristics. The similarities and differences between two treatment cohorts will be assessed using balance diagnostics tests. A stratified descriptive analysis will also be conducted at different time points to assess if the characteristics of the two exposures changes over time.										

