9.2 SETTING

This retrospective database study will leverage the GE EMR data from October 1, 2013 to April 30, 2018. The EMR consists of patient data from ambulatory care records in the US and is representative of the US population receiving healthcare in the ambulatory setting. Patients will be included in one of three study cohorts based on prescription history from October 1, 2014 to April 30, 2018, allowing for a 12-month pre-index period to describe patient demographic, clinical and treatment characteristics.

Index date

The index date for the nintedanib (or pirfenidone) cohort will be the date of the first nintedanib (or pirfenidone) prescription during the selection window (from October 1, 2014 to April 30, 2018). The index date for the untreated cohort will be the date of the earliest IPF diagnosis or a randomly assigned date between October 1, 2013 and April 30, 2018.

Pre-index period

[figure not shown]
The pre-index period for each cohort will be the 12 months prior to the index date. Patients will be required to have ≥ 1 diagnosis of IPF during the pre-index period (see additional inclusion criteria described below).

Post-index period

The post-index period for each cohort will start from the index date. Since the study aims to evaluate patient characteristics during the pre-index period, no minimum follow-up will be required for post-index period and no study measures will be assess during the post-index period.

Patient selection is illustrated in Figure 1.

Figure 1. Patient Selection

Nintedanib cohort

Inclusion criteria:

- With ≥ 1 diagnosis for IPF (the International Classification of Diseases, Ninth Revision, Clinical Modification [ICD-9-CM] codes 516.3, 516.31, 515,¹¹ or ICD-10-CM codes J84.112) in the EMR between October 1, 2013 to April 30, 2018
- With ≥ 1 prescription for nintedanib between October 1, 2014 and April 30, 2018 (the selection window)
 - The date of the first prescription will be defined as the index date
- With ≥ 1 record in the EMR database during the 12 months prior to the index date (the pre-index period)
- With ≥ 1 diagnosis of IPF during the 12 months prior to the index date
- Age ≥ 40 on the index date
- will explore also requiring ≥ 1 chest CT scan before first IPF diagnosis during the pre-index period¹²

Exclusion criteria:

- With ≥ 1 diagnosis of other known causes of interstitial lung disease (ILD) on the date of or after the first IPF diagnosis during the pre-index period^{12,13}

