- Other known causes of ILD include conditions such as systemic sclerosis, rheumatoid arthritis, systemic lupus erythematosus, dermatomyositis, polymyositis, Sjögren disease, and hypersensitivity pneumonitis (ICD-9-CM codes 135, 237.7, 272.7, 277.3, 277.8, 446.21, 446.4, 495, 500–505, 506.4, 508.1, 508.8, 516.0, 516.1, 516.32–516.37, 516.2, 516.8, 516.9, 517.0, 517.2, 517.8, 518.3, 555, 710.0, 710.0–710.4, 714.0, 714.81, 720, and 759.5, or ICD-10-CM equivalent codes)^{12,13}
- With ≥ 1 prescription for nintedanib prior to the index date
- With ≥ 1 prescription for pirfenidone prior to or on the index date

Pirfenidone cohort

Inclusion criteria:

- With ≥ 1 diagnosis for IPF (ICD-9-CM codes 516.3, 516.31, 515,¹¹ or ICD-10-CM codes J84.112) in the EMR between October 1, 2013 to April 30, 2018
- With ≥ 1 prescription for pirfenidone between October 1, 2014 and April 30, 2018 (the selection window)
 - The date of the first prescription will be defined as the index date
- With ≥ 1 record in the EMR database during the 12 months prior to the index date
- With ≥ 1 diagnosis of IPF during the 12 months prior to the index date
- Age ≥ 40 on the index date
- will explore also requiring ≥ 1 chest CT scan before first IPF diagnosis during the pre-index period¹²

Exclusion criteria:

- With ≥ 1 diagnosis of other known causes of interstitial lung disease (ILD) on the date of or after the first IPF diagnosis during the pre-index period^{12,13}
 - Other known causes of ILD include conditions such as systemic sclerosis, rheumatoid arthritis, systemic lupus erythematosus, dermatomyositis, polymyositis, Sjögren disease, and hypersensitivity pneumonitis (ICD-9-CM codes 135, 237.7, 272.7, 277.3, 277.8, 446.21, 446.4, 495, 500–505, 506.4, 508.1, 508.8, 516.0, 516.1, 516.32–516.37, 516.2, 516.8, 516.9, 517.0, 517.2, 517.8, 518.3, 555, 710.0, 710.0–710.4, 714.0, 714.81, 720, and 759.5, or ICD-10-CM equivalent codes)^{12,13}
- ≥ 1 prescription for pirfenidone prior to the index date
- ≥ 1 prescription for nintedanib prior to or on the index date

Untreated cohort

Inclusion criteria:

- With ≥ 1 diagnosis for IPF (ICD-9-CM codes 516.3, 516.31, 515,¹¹ or ICD-10-CM codes J84.112) in the EMR between October 1, 2013 to April 30, 2018
 - Index date will be defined as the date of the earliest IPF diagnosis or a randomly assigned date based on the exploratory analyses to be performed on the two treatment cohorts (exploring time from IPF diagnosis to treatment initiation)

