9.3.2 Outcomes

9.3.2.1 Primary outcomes

The primary outcome will be the ASD and p-value comparing baseline patient characteristics (as described in section 9.3.3) between the following cohorts:

- Nintedanib vs. pirfenidone
- Nintedanib vs. untreated
- Pirfenidone vs. untreated

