9.3.3 Covariates

The following measures will be evaluated during the 12-month baseline period, including index date, unless otherwise noted. Measures will be reported separately for each of the three cohorts.

For nintedanib and pirfenidone cohorts only:

- Index medication (n, %)
 - Nintedanib
 - Pirfenidone
- Average daily dose of the index prescription
 - Nintedanib (mean, SD, median, min, max) and categories (n, %)
 - 100 mg
 - 150 mg
 - Unknown
 - Pirfenidone (mean, SD, median, min, max) and categories (n, %)
 - 267 mg
 - Unknown
- Time from the earliest diagnosis for IPF to index (mean, SD, median, min, max)
- Prescribing physician specialty (n, %)
 - Primary care
 - Internal medicine
 - Pulmonologist
 - Other

For all cohorts:

Demographic characteristics

- Age (mean, SD, median, min, max) and age categories on index date (n, %)
 - 40-49
 - 50-59

- 60-69
 - ≥ 70
- Gender (n, %)
 - Male
 - Female
- Index year (n, %)
 - 2014
 - 2015
 - 2016
 - 2017
 - 2018
- Region (n, %)
 - Northeast
 - Midwest
 - South
 - West
- Race/ethnicity (n, %) (expected to be missing for about 40% of patients)
 - White
 - African American
 - Hispanic
 - Asian
 - Other
 - Unknown
- Payer type (n, %)
 - Commercial
 - Medicaid
 - Medicare
 - Self-Insured
 - Other/Unknown

Clinical characteristics (based on ICD-9/10-CM procedure and diagnosis codes, laboratory test codes, CPT codes and NDC/RxNorm (to be included in Appendix), as well as other information in the EMR encounter files)

- Body weight (lbs; mean, SD, median, min, max)
 - Body mass index (BMI; kg/m²; mean, SD, median, min, max)
 - BMI category, defined using BMI field (n, %)
 - Underweight ($<18.5 \text{ kg/m}^2$)
 - Normal weight (18.5 to 24.99 kg/m²)
 - Overweight (25 to 29.99 kg/m²)
 - Obese (30 to 34.99 kg/m²)
 - Very obese ($\geq 35 \text{ kg/m}^2$)

- Blood pressure (BP)¹⁴ (n, %)
 - Diastolic BP
 - Normal (<80 mmHg)
 - High (≥ 80 mmHg)
 - Systolic BP
 - Normal (<120 mmHg)
 - Elevated (≥ 120 and < 129 mmHg)
 - High (≥ 130 mmHg), further broken down as follows if data allow
 - Stage 1 (≥ 130 and < 139 mmHg)
 - Stage 2 (≥ 140 mmHg)
- Smoking status at index (n, %); excluding smokeless tobacco; categories to be finalized during analysis
 - Smoker
 - Non-smoker, further broken down as follows if data allow
 - Previous smoker
 - Never smoker
 - Unknown/missing
- Alcohol consumption (n, %)
 - Yes
 - No
 - Unknown/missing

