For the second objective, the probabilities of receiving one treatment over another (or nintedanib or pirfenidone vs. untreated) will be tested by propensity scores (PS) and using multivariable logistic regression (possibly with stepwise selection) after controlling for key baseline characteristics (selected based on significance in bivariate analysis or face validity, e.g. age). The similarities and differences between the exposure cohorts will be assessed using balance diagnostics tests (e.g., graphical distribution of overlap between propensity scores of two cohorts (histograms, boxplots), percentage of sample matched, Pearson’s correlation coefficient, standardized differences, density estimates, c-statistics, receiver operating characteristic [ROC] curves). Ninety-five percent confidence intervals will be calculated for key parameters. Statistical tests will be two-sided, with α -level of 0.05 for statistical significance.

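### Time since IPF diagnosis is planned for the treated cohorts only, so no output shows whether untreated index dates line up with treatment initiation

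*Combined protocol and SAP*

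**What the plan says.** Section 9.3.3 (Covariates) has two blocks. The first, headed "For nintedanib and pirfenidone cohorts only", contains "Time from the earliest diagnosis for IPF to index (mean, SD, median, min, max". The second block, for all cohorts, has no measure of disease duration, and Section 9.7.1 does not add one. The abstract describes the same variable as "time from the earliest diagnosis of IPF to index medication". That wording has no meaning for a patient without an index medication, so the restriction looks intended rather than a layout slip.

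Section 9.2 leaves the untreated index date open. The general text gives "the date of the earliest IPF diagnosis or a randomly assigned date between October 1, 2013 and April 30, 2018". The untreated inclusion criteria give first diagnosis or "a randomly assigned date based on the exploratory analyses to be performed on the two treatment cohorts", and explain that those analyses explore the time from diagnosis to treatment start.

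Section 9.3.2.1 makes "Nintedanib vs. untreated" and the matching pirfenidone contrast primary outcomes. Section 9.3.2.2 adds a propensity score for any antifibrotic against none. Section 9.7.1 treats an ASD of at least 10% as meaningful, uses p-values to help identify key drivers of treatment selection, and fits models "controlling for key baseline characteristics", chosen by bivariate significance or face validity.

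**The concern.** Every baseline characteristic is anchored to the index date. For treated patients that date is an event in the course of disease; for untreated patients it is assigned. Section 7 calls IPF progressive, with median survival of 2.5 to 3.5 years from diagnosis. Oxygen therapy, lung function, steroid use and coded comorbidity can therefore be expected to shift with time since diagnosis. If the cohorts are measured at different durations, some of their differences reflect timing rather than treatment choice.

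The plan appears to see this, because one of its options ties the untreated date to the treated delays. Yet it plans no output showing whether alignment was achieved, and neither Section 9.9 (Limitations) nor Section 9.12 (Bias) mentions duration. With about 10,000 untreated patients, a modest timing effect could be reported as a meaningful and significant driver of treatment.

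**Working it through.** The documents give no duration figure to reproduce. The check is therefore a reading of the sections above, plus illustrations using the ASD and CI formulas of Section 9.7.1.

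**Precision.** Inputs (abstract): 615 nintedanib, 868 pirfenidone, about 10,000 untreated. The formula is σ[d] = √((n1+n2)/(n1·n2) + d²/(2(n1+n2))). At d = 0.10:
- 615 vs 10,000: σ = 0.0416, 95% CI 0.019 to 0.181.
- 868 vs 10,000: σ = 0.0354, 95% CI 0.031 to 0.169.

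An ASD at the threshold would thus also be statistically significant.

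**Duration ASD.** Assumptions, none of them from the documents:
- Diagnosis dates are uniform over the 55 months from October 2013 to April 2018.
- Treated delay is exponential with mean 3, 6 or 9 months.
- Treated index dates fall between October 2014 and April 2018, which leaves observed delays (mean, SD) of 2.98 (2.95), 5.66 (5.40) and 7.80 (7.15) months.

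| Untreated index date | Duration ASD (treated mean 3 / 6 / 9 months) |
|---|---|
| Drawn from the treated delays, same window | 0.00 to 0.09 over all cases |
| Unrelated to treated delay, both arms limited to 12 months since diagnosis | 1.06 / 0.56 / 0.38 |
| Unrelated, any time after diagnosis, uniform from October 2014 | 1.72 / 1.36 / 1.08 |
| First diagnosis (duration 0, SD 0) | 1.43 / 1.48 / 1.54 |

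Worked entries:
- Third row: untreated mean 19.04, SD 12.86, so (19.04 − 2.98)/√((12.86² + 2.95²)/2) = 16.06/9.33 = 1.72.
- Second row: untreated mean 5.99, SD 3.46, and treated mean 2.78, SD 2.50, so 3.21/3.02 = 1.06.
- Fourth row: the formula reduces to √2 × mean/SD of the treated delay. That is 1.41 for an untruncated exponential, and 2.83 to 0.47 as SD/mean runs from 0.5 to 3.

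The middle rows depend on how a date is kept after diagnosis. Drawing it uniformly between diagnosis (or October 2014 if later) and April 2018 lowers the third row to 1.26 / 0.91 / 0.65 and the second to 0.69 / 0.22 / 0.05.

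**Spillover.** Assume oxygen use is 20% at diagnosis and rises by 0.5 or 1 percentage point per month in every cohort.
- Third row, treated mean 3, slope 0.5: 29.5% vs 21.5%, ASD = 0.080/0.434 = 0.185. Over the whole row the range is 0.13 to 0.35.
- Second row: 0.02 to 0.08, all below the threshold.

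For the first-diagnosis rule, take a characteristic present in 10% at diagnosis and accruing at 0.10 per year. Measuring treated patients 6 months later gives 1 − 0.9·e^(−0.05) = 14.4%, ASD 0.134. Starting from 20%, the ASD is 0.094.

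**A further check the variable would give.** The random window in the general text of Section 9.2 starts in October 2013, and that sentence does not say the date must follow diagnosis. If both dates were uniform over the window, about half the assigned dates would precede diagnosis. Negative values would show this at once.

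**The case against.** The strongest reply is that the untreated inclusion criteria tie the random date to the treated delays, so alignment is built in and the duration ASD is near zero. This stands as to size. It does not supply the missing check, and the plan does not commit to that option.

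Section 9.2 also requires an IPF diagnosis in the 12 months before index for each cohort. Read strictly, this bounds the gap and keeps the oxygen illustration below 10%. The bound is uncertain: the untreated criteria do not repeat the requirement, and repeat coding can satisfy it long after first diagnosis. The delays and slopes used above are also assumed. Both drugs were approved only on 15 October 2014 (Section 9.3.1), so patients diagnosed earlier had to wait. Longer treated delays would shrink the gap under random dates.

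Three stronger readings are tempting, and the documents do not support them.
- A reader might infer that duration is barred from the propensity model. It is only unplanned: selection by face validity could admit it, and diagnosis dates are available.
- A reader might infer that untreated differences cannot be separated from disease stage at all. FVC, DLCO, oxygen saturation, GAP and oxygen therapy are listed for all cohorts. They are partial substitutes: GAP depends on the data allowing it and uses no duration. In Table 1, of 1,231 treated patients with a lung-function or saturation value, 293 have a DLCO value and 627 an FEV/FVC value.
- A reader might infer that a large bias is shown. The large figures need index dates unrelated to the treated delays or fixed at first diagnosis.

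**Conclusion.** The point holds as a gap in the planned outputs. The treated-versus-untreated ASD tables contain no duration measure, and nothing shows whether the untreated index dates are aligned with treatment initiation. The nintedanib-versus-pirfenidone contrast is unaffected.

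The size of any imbalance is unknown. On the stated assumptions the duration ASD runs from about 0 to 0.1 (dates drawn from treated delays), through about 0.4 to 1.1 (unrelated dates within 12 months) and 1.1 to 1.7 (unrestricted random dates), to 1.4 to 1.5 (index at first diagnosis). The two middle ranges fall under other ways of placing the date. Spillover to other characteristics may or may not cross 10%. That spread is the reason to report the variable: it is the direct evidence of which case applies.

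The remedy has limits. Data start in October 2013, so the variable measures time since the first recorded code, not true disease duration. Under the first-diagnosis rule it is zero for every untreated patient, so there is no overlap to adjust on. Under a draw from treated delays, its model coefficient partly reflects the sampling rule rather than a driver of treatment, so forcing it into the model in every case is not justified.

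**What to change.** 1. In Section 9.3.3, move the variable to the all-cohorts block. Define it identically in all three cohorts as time from the first recorded IPF code in the data window to index, and note left-truncation at October 2013.
2. Report its ASD and 95% CI for both untreated contrasts, labelled as the check on index-date assignment.
3. Settle the untreated index rule in Section 9.2, since the meaning of the check depends on it.
4. If a random date is used and the ASD is still at least 10%, include the variable in the treated-versus-untreated model, at least as a sensitivity analysis.
5. If the first-diagnosis rule is used, state in the report that the untreated contrasts are not at equal time since diagnosis and that adjustment cannot correct this.

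The cost is one line moved, one row added to two comparisons, and at most one extra model fit. No new data are needed, because IPF diagnosis dates are already required to select the untreated cohort.

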7. RATIONALE AND BACKGROUND

Idiopathic Pulmonary Fibrosis (IPF) is a specific form of chronic, progressive fibrosing interstitial pneumonia of unknown cause, occurring primarily in older adults, and limited to the lungs.¹ IPF is a debilitating, life limiting condition with a median survival range of 2.5 to 3.5 years from the time of diagnosis.² A study using insurance claims data from the United States estimated the incidence of IPF to be between 6.8 and 16.3 per 100,000 persons.³ The same study yielded a prevalence estimate of between 14.0 and 42.7 per 100,000 persons, depending on the case definition used.³ The economic burden of IPF is significant, with the annual medical cost (hospitalization, emergency room [ER] visits, outpatient visits, and use of procedures and tests) to the US healthcare system estimated at close to \$2 billion in 2012.⁴

The goals of treatment for IPF are to stop disease progression, reduce symptoms, prevent acute exacerbations, and prolong survival.⁵ Pulmonary rehabilitation and oxygen treatment are commonly utilized as supportive treatments, and lung transplant surgery may be considered in some patients.⁵ Many pharmacological treatments (i.e. anticoagulants, combination of N-acetylcysteine, prednisone and azathioprine, selective endothelin receptor) have been evaluated in IPF patients; however, international guidelines recommend against the use of these treatments due to insufficient evidence.⁶ The treatment options for patients with IPF changed significantly in October 2014 when the FDA approved two products that slowed disease progression, Ofev (nintedanib, Boehringer Ingelheim) and Esbriet (pirfenidone, Genentech).^{7,8} Recently updated American Thoracic Society/European Respiratory Society/Japanese Respiratory Society, and Latin American Thoracic Association clinical practice guidelines gave conditional recommendations for the use of nintedanib and pirfenidone in the majority of patients with IPF.⁶

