- Charlson comorbidity index (CCI)¹⁵ (mean, SD, median, min, max) and categories (n, %), defined using ICD diagnosis codes
 - 0
 - 1
 - 2
 - 3
 - 4+
- Respiratory comorbidities¹⁶ (n, %), defined using ICD diagnosis codes
 - COPD (Chronic obstructive pulmonary disease), includes chronic bronchitis and emphysema
 - Pulmonary hypertension
 - Obstructive sleep apnea
 - Lung cancer
 - Pulmonary embolism
 - Asthma
 - Acute respiratory distress syndrome
 - Pulmonary edema
 - Cough
 - Upper respiratory tract infection (includes acute bronchitis)
 - Bronchitis (not specified as acute or chronic)

- Sinusitis
- Gastroesophageal reflux disease (GERD) (n, %), defined using ICD diagnosis codes
- Metabolic disorders¹⁶ (n, %), defined using ICD diagnosis codes
 - Obesity (defined as ICD-9 code 278.0 or ICD-10 code E66 or BMI ≥ 30 kg/m²)
 - Diabetes
 - Any diabetes
 - Type 1 diabetes
 - Type 2 diabetes¹⁶
 - Dyslipidemia (includes hypercholesterolemia and hyperlipidemia)
- Cardiovascular disorders¹⁶ (n, %), defined using ICD diagnosis codes
 - Arrhythmia
 - Atrial fibrillation
 - Heart failure
 - Ischemic heart disease
 - Stroke
 - Hypertension (includes systemic arterial hypertension)
 - Peripheral arterial diseases
 - Cardiomyopathy
- Mental disorders (n, %), defined using ICD diagnosis codes
 - Depression
 - Anxiety
 - Schizophrenia
 - Dementia
 - Bipolar disorders
- Renal impairment (n, %), defined using ICD diagnosis codes
- Hepatic impairment (n, %), defined using ICD diagnosis codes
- Laboratory measures (to the extent that the data allow; tests will be identified by procedure codes and EMR data fields; if repeated measurements of a test are observed, the one closest to the index date will be reported, with the exception of several renal and liver measures (where noted) when any evidence of patient history of the condition during baseline will take precedent over the measure closest to index)
 - Anticoagulation tests (n, %)
 - Prothrombin time (n, %)
 - High (>14 seconds)
 - Normal (10-14 seconds)
 - Low (<10 seconds)
 - Activated partial thromboplastin time (aPTT; n, %)
 - Normal (30-40 seconds)
 - Elevated (41-70 seconds)

- Critical (>70 seconds)
- Bleeding time (n, %)
 - Normal (1-9 minutes)
 - Platelet dysfunction (10-15 minutes)
 - Critical (>15 minutes)
- Hematologic markers
 - Blood hemoglobin (mean, SD, median, min, max)
 - Blood hematocrit (mean, SD, median, min, max)
 - Red blood cell count (mean, SD, median, min, max)
 - Platelet count (n, %)

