 - Low (<150,000 platelets/mcL)
 - Normal (150,000-450,000 platelets/mcL)
 - High (>450,000 platelets/mcL)
 - Conventional C - reactive protein (n, %)
 - Normal (≤ 5.0 mg/L)
 - High (>5.0 mg/L)
- Liver function tests (n, %)
 - Alanine transaminase (ALT; n, %); patient history of high ALT level suggesting hepatic impairment will be reported and take precedent to ALT value closest to index
 - Low (<7 U/L)
 - Normal (7 – 56 U/L)
 - High (>56 U/L)
 - Aspartate transaminase (AST; n, %); patient history of high AST level suggesting hepatic impairment will be reported and take precedent to AST value closest to index
 - Low (<5 U/L)
 - Normal (5 – 40 U/L)
 - High (>40 U/L)
 - Alkaline phosphatase (ALP; n, %)
 - Low (<44 IU/L)
 - Normal (44 – 147 IU/L)
 - High (>147 IU/L)
 - Gamma-glutamyl transpeptidase (GGT; n, %)
 - Low (<9 U/L)
 - Normal (9-48 U/L)
 - High (>48 U/L)
 - Total bilirubin (n, %); patient history of high bilirubin level suggesting hepatic impairment will be reported and take precedent to value closest to index
 - Low (<0.2 mg/dL)

- Normal (0.2-1.2 mg/dL)
 - High (>1.2 mg/dL)
 - Kidney function tests (n, %)
 - Albumin to creatinine ratio (ACR; n, %)
 - Normal (<30)
 - Microalbuminuria (30-300)
 - Macroalbuminuria (>300)
 - Glomerular filtration rate (GFR; n, %); patient history of low GFR suggesting renal impairment will be reported and take precedent to value closest to index
 - Low (<90 mL/min/1.73m²)
 - Normal (90 – 120 mL/min/1.73m²)
 - High (>120 mL/min/1.73m²)
 - Serum creatinine (mean, SD, median, min, max); patient history of high serum creatinine level suggesting renal impairment will be reported and take precedent to value closest to index
 - Cholesterol levels (n, %)
 - Total cholesterol (mg/dL; n, %)
 - Normal (<200 mg/dL)
 - Borderline high (200-239 mg/dL)
 - High (\geq 240 mg/dL)
 - Triglyceride (mg/dL; n, %)
 - Normal (<150 mg/dL)
 - Borderline high (150-199 mg/dL)
 - High (\geq 200 mg/dL)
 - Cholesterol in high-density lipoprotein (HDL; n, %)
 - Normal (\geq 40 mg/dL)
 - Abnormal (<40 mg/dL)
 - Cholesterol in low-density lipoprotein (LDL; n, %)
 - Normal (<100 mg/dL)
 - Borderline high (100 – 159 mg/dL)
 - High (\geq 160 mg/dL)
- Pulmonary function tests (PFTs) indicative of IPF severity (n, %)
 - FVC (n, %)
 - Normal (\geq 80%)
 - Abnormal (<80%)
 - Forced expiratory volume in one second (FEV1) /FVC ratio (n, %)
 - Normal (\geq 70%)
 - Abnormal (<70%)
 - Total lung capacity (TLC) (mean, SD, median, min, max)

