9.7.1 Main analysis

For the primary objective, baseline patient characteristics will be described using descriptive analysis, i.e. described as counts and percentages for categorical variables (e.g. gender, race, comorbidities, treatments, diagnostic tests performed) and measures of central tendency (mean, median, SD, and min/max) for continuous variables (e.g., age, lab measures values, BMI). Differences between the cohorts will be assessed using ASD, where an ASD of at least 10% will be considered a meaningful difference.²² Patients with missing data will be reported as missing and excluded from the comparison for the missing variable.

For continuous variables, the standardized differences will be calculated as

$$d = \frac{(\bar{X}_1 - \bar{X}_2)}{\sqrt{\frac{s_1^2 + s_2^2}{2}}}$$

Where \bar{X} denote sample means in each exposure cohort, and s denotes sample variances.

For categorical variables, the standardized differences will be calculated as

$$d = \frac{(p_1 - p_2)}{\sqrt{\frac{[p_1(1 - p_1) + p_2(1 - p_2)]}{2}}}$$

Where p denotes proportion of a binary baseline variable in the two exposure cohorts.

The confidence intervals (CIs) for standardized differences will also be calculated as defined below:

$$95\% CI = d \pm 1.96 \times \sigma [d]$$

$$\text{where, } \sigma [d] = \sqrt{\frac{n_1 + n_2}{n_1 \times n_2} + \frac{d^2}{2(n_1 + n_2)}},$$

Where n_i denotes sample sizes of each exposure cohort.

Bivariate statistical significance tests such as Chi-square test for categorical variables and Wilcoxon rank sum test or t-test for continuous variables (depending on distribution of data) will also be performed to compare differences in baseline characteristics between the three cohorts. In addition to standardized differences, p-value in comparing characteristics between the three cohorts will also be reported to help identify “key drivers” associated with treatment selection.

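### A single GFR band below 90, read as suggesting renal impairment, is non-specific and strongly dilutes a cohort difference confined to impaired patients; GFR should also be summarised as a continuous value

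*Combined protocol and SAP*

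**What the plan says.** Section 9.3.3 (Covariates, kidney function tests) reports GFR as n and % in three categories. The lowest is "Low (<90 mL/min/1.73m²", the next is "Normal (90 – 120 mL/min/1.73m²", and the third covers values above 120. No finer band is given below 90, and no mean, SD or median is listed.

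The GFR line ties the low category to a clinical meaning: "patient history of low GFR suggesting renal impairment will be reported and take precedent to value closest to index". The introduction to the laboratory measures states the general rule for several renal and liver tests, "when any evidence of patient history of the condition during baseline will take precedent over the measure closest to index". No level other than 90 is offered for what counts as low.

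Three other renal measures stand in the same section: "Renal impairment (n, %), defined using ICD diagnosis codes"; albumin to creatinine ratio (ACR) in three levels; and serum creatinine with mean, SD, median, min and max, where "patient history of high serum creatinine level suggesting renal impairment will be reported and take precedent to value closest to index".

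The population is aged 40 or over, and section 7 describes the disease as "occurring primarily in older adults, and limited to the lungs". Section 9.7.1 sets the decision rule: "an ASD of at least 10% will be considered a meaningful difference".

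**The concern.** In an older population a large share of patients can be expected below 90. A GFR of 88 and a GFR of 25 are then the same result, and the category separates a minority with higher GFR from everyone else. That is a weak marker of renal impairment, which is the meaning the plan gives it. This comes from the cut itself and holds with one test per patient; the rule that any low baseline value takes precedence can only enlarge the Low group.

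The study's purpose is to find characteristics that separate the cohorts. If one cohort holds more patients with clearly reduced GFR, but the rest of the distribution is alike, the GFR row could fall under the 10% threshold and be reported as no meaningful difference. Section 9.7.1 selects model covariates on bivariate significance or face validity, so a diluted GFR variable is also a weaker candidate for the propensity model.

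**Working it through.** **Inputs from the documents.** The cut at 90, the ASD formulas and the 10% threshold. The plan gives no GFR mean, SD or share below 90, so there is no figure of its own to reproduce.

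**Assumptions.** Reference cohort: GFR normal with (mean, SD) of (65, 18), (70, 20), (75, 20) or (80, 20), plus (85, 20) as a check with better renal function. Comparison cohort: 90% of the same distribution plus 10% from a normal with mean 40 and SD 10. The cut of 60 is illustrative and is not in the documents.

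**Formulas.**
- Share below a cut c: p₁ = Φ((c − mean)/SD).
- Comparison cohort: p₂ = 0.9·p₁ + 0.1·Φ((c − 40)/10).
- Binary ASD (section 9.7.1): |p₁ − p₂| / √{[p₁(1 − p₁) + p₂(1 − p₂)]/2}.
- Continuous ASD (section 9.7.1): |difference in means| / √{(s₁² + s₂²)/2}.

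**One case in full, mean 75 and SD 20.**
- At 90: p₁ = Φ(0.75) = 0.773 and p₂ = 0.9 × 0.7734 + 0.1 × 1.000 = 0.796. ASD = 0.0226 / √[(0.1753 + 0.1624)/2] = 0.055.
- Continuous: the comparison mean is 0.9 × 75 + 0.1 × 40 = 71.5. Its variance is 0.9 × (400 + 5625) + 0.1 × (100 + 1600) − 71.5² = 480.25. ASD = 3.5 / √[(400 + 480.25)/2] = 0.167.

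**All cases, an extra 10% of impaired patients.**

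| mean, SD | % below 90 | ASD at 90 | ASD at 60 | ASD, continuous |
|---|---|---|---|---|
| 65, 18 | 92 | 0.031 | 0.119 | 0.135 |
| 70, 20 | 84 | 0.044 | 0.141 | 0.145 |
| 75, 20 | 77 | 0.055 | 0.171 | 0.167 |
| 80, 20 | 69 | 0.068 | 0.206 | 0.187 |
| 85, 20 | 60 | 0.083 | 0.246 | 0.206 |

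The 90 cut stays under 0.10 in every row, and the continuous value exceeds it in every row.

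**Where the 90 cut does respond** (the four main distributions, in the same order).
- Whole distribution lower by 5 units: ASD at 90 is 0.14, 0.16, 0.17 and 0.19, all above 10%.
- An extra 20% of impaired patients instead of 10%: ASD at 90 is 0.063, 0.091, 0.113 and 0.138, above 10% in two of the four.

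**Information kept by each cut for a small mean shift**, φ(z)²/[p(1 − p)] with z = (c − mean)/SD, relative to the continuous value:
- at 90: 31%, 44%, 52% and 58%;
- at 60: 62%, 58%, 52% and 44%.

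Neither cut is better throughout. The continuous value avoids the loss.

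**The case against.** A reader might infer that the GFR row cannot show any real renal difference between the cohorts. The documents and the arithmetic do not support that. A shift of the whole distribution is picked up at 90, and a large enough excess of impaired patients passes 10% in some cases. The dilution is specific to a moderate difference confined to the impaired tail.

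Nor is the study blind to renal function. Coded renal impairment, ACR and continuous serum creatinine are all planned, and any of them could reveal the difference or enter the model. That limits the harm, although none of them makes the GFR row measure what its wording says.

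The claim that GFR would be dropped from the model is also weaker than it looks. Section 9.7.1 allows selection on face validity as well as on bivariate significance, and the ASD threshold is not stated as a selection rule. GFR could be screened out, but it need not be.

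The GFR distributions are assumptions. The documents support only age 40 or over and a disease mainly of older adults. At a mean of 85 and SD 20 the share below 90 falls to about 60%, but the ASD at 90 is still only 0.083, so the conclusion does not need an extreme share below the cut.

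Finally, Low, Normal and High is the layout used for several other laboratory tests, and a cut at 60 would also discard information. Both points are fair, and they favour a continuous summary over replacing one cut with another.

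**Conclusion.** The point holds as a limited one. With a single band below 90 and no continuous summary, GFR is a non-specific marker of renal impairment. Under the four main assumed distributions, an extra 10% of patients with GFR near 40 gives an ASD of 0.03 to 0.07 at 90, under the plan's own threshold. The same difference gives 0.14 to 0.19 on the continuous value and 0.12 to 0.21 at an illustrative cut of 60. These sizes rest on assumed normal distributions and on a difference confined to impaired patients. The definition of Low, its link to renal impairment and the lack of a continuous summary rest on the text alone. This is a cheap improvement to one covariate and does not threaten the study's main conclusions.

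**What to change.** In section 9.3.3:

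1. Add a continuous summary of the GFR closest to index (mean, SD, median, min, max), as is already planned for serum creatinine.
2. Split the Low band into finer reporting bands, for example below 30, 30 to 59 and 60 to 89.
3. Use the continuous value as the main GFR measure in the ASD tables and as the candidate for the propensity model. Where the record holds only a reporting limit (such as above 60), use the banded version.
4. Do not use below 90 alone as the renal-impairment flag, and state which GFR level the history rule refers to.

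The cost is a few extra table rows from data already to be extracted. The lowest band may be sparse in the two treated cohorts.
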